		11.3.1 REDCap confidentially	
12	Data	Handling and Record Keeping	
	12.1	Data Capture Methods	
	12.2	Types of Data	59
	12.3	Storage of data	
	12.4	Study Records Retention	60
	12.5	Protocol Deviations	
13	INSU	RANCE & Finances	62
14	Public	cation Policy	63
15		ture References	
16	Appe	ndix	68
		C Serious Adverse Event Form	
	REDO	Cap Pre-screening questionnaire	72

LIST OF ABBREVIATIONS

ACL Australian Clinical Labs

AE Adverse Event/Adverse Experience

BAI Beck Anxiety Inventory

BIS-11 Barratt Impulsivity Scale version 11
CBT Cognitive Behavioural Therapy

CGI - I/S Clinical Global Impression scale - improvement/severity

CRF Case Report File

CTC Clinical Trial Coordinator

DQES v2 Dietary questionnaire for epidemiological studies version 2

ERP Exposure response prevention

GCP Good Clinical Practice

GMP Goods Manufacturing Practice
HAM-D Hamilton depression rating scale

ICH Requirements for Pharmaceuticals for Human Use

IEC Independent Ethics Committee
IICF Informant Information Consent Form

IP Investigational Product
IRB Institutional Review Board

N Total number of participants in population

NAC N-acetylcysteine

OCD Obsessive-Compulsive Disorder

PGI – I/S Patient Global Impression scale - improvement/severity

PI Principal Investigator

PICF Participant Information Consent Form

RA Research assistant

RCT Randomised, controlled trial

SAFTEE Systematic assessment for treatment emergent side effects SCID-5-CT Structured clinical interview for DSM-5 Clinical Trial version

SDS Sheehan Disability Scale

SNP Single nucleotide polymorphisms
SOP Standard Operating Procedure
TR-OCD Treatment refractory OCD

WHOQOL-BREF World Health Organisation Quality of Life-BREF Y-BOCS Yale-Brown Obsessive-Compulsive Scale

......

PROTOCOL SUMMARY

Title: N-acetylcysteine augmentation (NAC) in Obsessive-Compulsive disorder (OCD): A 24 week, randomised, double blind, placebo controlled trial

Phase: III

Population: Male and female adults (18-75 years old) with Obsessive-Compulsive Disorder (N = 200) located in Australia.

Number of Sites: (3) The University of Melbourne (The Melbourne Clinic); The University of Queensland (Royal Brisbane and Women's Hospital); Western Sydney University (National Institute of Complementary Medicine; NICM)

Study Duration: 2016 - 2019

[figure not shown]
Subject Participation Duration: 24 weeks

Description of Agent: N-acetylcysteine (NAC) is an acetylated form of the essential amino acid cysteine. NAC possess glutamate modulating activity and is the rate limiting substrate for glutathione (GSH) production, a potent endogenous antioxidant. Participants will take NAC or matching placebo (capsule form) orally in doses between 2,000mg – 4,000mg per day, depending on individual treatment response.

Description of Study Design: 20 week, randomised, double blind placebo controlled trial with a 4-week, single blinded, placebo run out

Estimated Time to Complete Enrollment: 3.5 years

Schematic of Study Design:

Assessment Schedule

	Baseline 1	Baseline 2	W4	W8	W12	W16	W20	W24
PICF	Х							
Demographics	Х							
Medical hx	Х							
Treatment hx/review	Х	Х	Х	Х	Х	Х	Х	Х
Caffeine, drug &								
alcohol intake	X		X	Х	Х	Х	X	X
Blood pressure		Х	Х	Х	Х	Х	Х	Х
NetSCID-5		Х						
Qualitative review			Х	Х	Х	Х	Х	Х
Y-BOCS sx checklist	Х	X*	Х	Х	Х	Х	Х	Х
Y-BOCS	Х	X*	Х	Х	Х	Х	Х	Х
DOCS	Х		Х	Х	Х	Х	Х	Х
SIGHD-17	Х		Х	Х	Х	Х	Х	Х
BIS-11	Х							

	Baseline 1	Baseline 2	W4	W8	W12	W16	W20	W24
BAI	Х		Х	Х	Х	Х	Х	Х
SDS	Х		Х	Х	Х	Х	х	Х
WHOQOL-BREF	Х				Х		х	
DQES v3.2		Х						
CGI-I			Х	Х	Х	Х	Х	Х
CGI-S		Х	Х	Х	Х	Х	Х	Х
PGI-S	Х		Х	Х	Х	Х	Х	Х
PGI-I			Х	Х	Х	Х	Х	Х
SAFTEE			Х	Х	Х	Х	Х	х
ВМІ		Х						
Blood collection		X**						

^{*}The Y-BOCS will be administered at baseline 2 if this appointment occurs more than seven days after baseline I visit **completed at any time point before conclusion of the study

2 BACKGROUND INFORMATION AND SCIENTIFIC RATIONALE

2.1 Background Information

Obsessive-Compulsive Disorder (OCD) is a debilitating neuropsychiatric disorder with an Australian prevalence of 1.9% (Slade, Johnston, Oakley Browne, Andrews, & Whiteford, 2009). It is characterised by repetitive and intrusive thoughts, urges or images (obsessions) and subsequent repetitive behaviours (compulsions), typically performed to mitigate the distress of the obsessions. The disorder is diverse in its symptomatic expression and ranges in severity; however, OCD is often chronic in nature, extremely debilitating and can greatly impair quality of life (APA, 2013; Subramaniam, Soh, Vaingankar, Picco, & Chong, 2013). Current first-line treatments for OCD are selective serotonin re-uptake inhibitors (SSRIs), often at higher doses than typically necessary for major depressive disorder, as well as psychological interventions, including exposure-response prevention (ERP) behavioural therapy. Additional augmentation strategies are often utilised including the use of anti-psychotics, the tricyclic antidepressant clomipramine (also used effectively as a monotherapy) and more recently, glutamatergic agents (McGrath et al., 2014). Despite these treatments eliciting beneficial effects in several cases, particularly when pharmacological and psychological strategies are employed concurrently, it is estimated that at least 40% of patients do not experience adequate responses to these therapies. and a greater portion still may continue to experience significant symptoms (Knopp, Knowles, Bee, Lovell, & Bower, 2013; McGrath et al., 2014; Pallanti, Grassi, & Cantisani, 2014).

[figure not shown]
2.1.1 OCD neurobiology and glutamate

Disturbed functioning of the cortical-striatal-thalamic-cortical (CSTC) circuits in the brain is regarded as the core pathophysiological feature of OCD, and remains one of the prime foci of neurobiological investigations (Harrison et al., 2013; Ting & Feng, 2011). These circuits appear hyperactive in OCD sufferers compared to healthy controls (Baxter et al., 1988; Nordahl et al., 1989; Swedo et al., 1989), become accentuated with symptom provocation (Adler et al., 2000; Breiter et al., 1996; Rauch et al., 1994), and attenuate with successful treatment for OCD symptoms (Benkelfat et al., 1990; Saxena et al., 2002).

The beneficial effects of clomipramine (with strong effects on the serotonergic system) for OCD was observed in clinical trials in the late 1970s, which promoted neurobiological investigations towards the serotonergic system neurotransmitter system (Ananth, Solyom, Bryntwick, & Krishnappa, 1979; Goodman, Grice, Lapidus, & Coffey, 2014). However, disparities within resulting neuroimaging studies, coupled with treatment resistance amongst patients to serotonin pharmaceutical agents, encouraged research towards other neurotransmitter systems, including dopamine and glutamate (Goodman, Grice, Lapidus, & Coffey, 2014). A converging body of genetic, neuroimaging, preclinical and clinical evidence highlights the contributing role of disturbances within the glutamate system and OCD (Pittenger, Bloch, & Williams, 2011) summarized in Table 2.1. However, various limitations and disparities exist in the currently available studies. For instance, sample sizes within the neuroimaging studies are often small and heterogeneous with respect to OCD chronicity, severity, co-morbid psychiatric disorders and medication status, all of which may affect observed neurobiological activity. Furthermore, difficulties in specifically assessing glutamate neurotransmitter activity may confound interpretation of these findings. For example, proton magnetic resonance spectroscopy (1H MRS) measures glutamate in a complex with glutamine (i.e. Glx), and does not differentiate between glutamate's structural and neurochemical properties (Pittenger, Bloch, & Williams, 2011). Thus, "glutamate abnormalities are considered potentially important in OCD, but technically difficult to assess" (Brennan, Rauch, Jensen, & Pope Jr., 2013). In addition, several other neuroimaging studies fail to show significant differences in Glx activity throughout various regions of the brain between people with OCD and healthy controls (Brennan, Rauch, Jensen & Pope, 2013; Simpson et al., 2015). Regardless, the available evidence does provide additional support for the heterogeneous neurobiological aetiology of OCD and the well recognised frontal striatal model of the disorder, which postulates heightened activity of direct neural pathways over indirect, both of which operate under glutamatergic neurotransmission (see Figure 2.1). Thus, regulation of glutamate transmission may be a beneficial treatment strategy for some patients with OCD.

12 DEC 2018

Figure 2.1 Involvement of glutamate in the cortical-striatal-thalamic-cortical circuitry

Adapted from Pauls, Abramovitch, Rauch, & Geller, 2014

Note. Solid black lines depict glutamate pathways and dashed lines depict GABA pathways. It is suggested that people with OCD have lower threshold activation for this system, which results in excessive activity of the direct pathway (striatum activation increases GABA signals to the globus pallidus interna (GPi) and substantia nigra (SNr)). This activity results in increased glutamatergic signals to the orbital frontal cortex (OFC) & anterior cingulate cortex (ACC), heightening the direct pathways positive feedback mechanisms. In OCD, increased tone of the direct pathway inhibits the modulating activity of the indirect pathway (glutamatergic signalling from the subthalamic nucleus (STN) to the GPi and SNr) and thus, results in disturbed glutamate neurotransmission.

Table 2.1 Summary of evidence for glutamate's role in OCD

Study Focus	Finding	Citation
Genetic	Polymorphisms of an NMDA subunit associated with OCD susceptibility	Arnold et al., 2004
	Glutamatergic gene variations associated with increased volume of the right ACC, left OFC and	Arnold et al., 2009
	thalamus in psychotropic-naive paediatric OCD patients	
	Strong evidence for variations in SLC1A1 gene (glutamate transporter gene) in OCD	Reviewed by Stewart et al., 2013
Preclinical	Stimulation of glutamatergic neurons in the OFC and VMS induced OCD like behaviour	Ahmari et al., 2013
	Stimulation of cortical-limbic glutamate output induces OCD like behaviour	McGarth et al., 2000
Neuroimaging	PET studies suggesting glutamate hyperactivity evident by increased glucose metabolism in	Baxter, et al., 1988; Swedo, et al.,
Studies	glutamatergic neurons of adults with OCD versus healthy controls	1989
	• 1H MRS study demonstrating reduced levels of Glx in the ACC in psychotropic naïve paediatric	Rosenberg et al., 2004
	sample	
	• 1H MRS study demonstrating greater levels of Glx in the right OFC correlating with symptom severity	Whiteside et al., 2006
	¹ H MRS study demonstrating reduced levels of Glx in the ACC in a cohort of females, independent	Yucel et al., 2008
	of medication status	
	 ¹H MRS study demonstrating increased levels of Glx in the left caudate nucleus in a paediatric 	Arnold et al., 2009
	cohort. Glx levels decreased after successful SSRI treatment	
	 ¹H MRS study demonstrating decreased levels of tNAA in the pACC versus controls. Levels 	O'Neil et al., 2012
	significantly increased after 4-weeks of intensive CBT and correlated with OCD symptom	
	improvement	
	PET imaging study demonstrating a positive correlation with mGluR5 DVR and obsession sub-score	Akkus et al., 2014
	of the Y-BOCS	
	Single voxel MRS study demonstrating decreased glutamate levels in mPFC and right thalamus in	Zhu et al., 2015
	unmedicated OCD patients significant over healthy controls	
	¹ H MRS study in paediatric sample of OCD + ASD demonstrated higher levels of glutamate in the	Naaijen et al., 2017
	ACC but not the striatum in both conditions versus healthy controls	

CSF studies	•	High levels of glutamate in the CSF of psychotropic naive adults with OCD, independent of age,	Chakrabarty, Bhattacharyya,
		gender, clinical severity or chronicity	Christopher & Khanna, 2005
	•	High levels of glutamate in CSF of adults with OCD. Higher binding of autoantibodies in the basal	Bhattacharyya et al., 2009
		ganglia and thalamus of brain	

ACC = anterior cingulate cortex; ASD = autism spectrum disorder; CSF = cerebral spinal fluid; DVR = distribution volume ratio; Glx = glutamate glutamine complex; 1H MRS = proton magnetic resonance spectroscopy; mGluR5 = metabotropic glutamate receptor 5; mPFC = medial prefrontal cortex; MRS = magnetic resonance spectroscopy; OCD = Obsessive-Compulsive Disorder; OFC = orbital frontal cortex; pACC = pregenual anterior cingulate cortex; PET = positron emission tomography; tNAA = N -acetyl-aspartate + N -acetyl-aspartyl-glutamate; VMS = ventromedial striatum; SSRI = Selective-serotonin reuptake inhibitor; Y-BOCS = Yale-Brown Obsessive Compulsive Scale

2.1.2 Oxidative stress in OCD

Various studies highlight greater levels of oxidative stress, lipid peroxidation and disturbances in antioxidant defense systems in blood samples of individuals with OCD versus healthy controls (see Figure 2.2) (Behl, Swami, Sircar, Bhatia, & Banerjee, 2010; Ersan, Bakir, Erdal Ersan, & Dogan, 2006; Kandemir, Abuhandan, Aksoy, Savik, & Kaya, 2013). Of interest, one study demonstrated that higher levels of oxidative stress correlated with symptom severity (Chakraborty, Singh, Dasgupta, Mandal, & Nath Das, 2009). Nevertheless, due to the crosssectional design of these studies, and absence of longitudinal data, whether oxidative stress is a cause or consequence of OCD pathophysiology is yet to be identified. In addition, and similarly to the neurobiological investigations regarding glutamate, other studies fail to demonstrate significant difference over healthy controls (Alici et al., 2016). Of interest, it has been postulated that the apparent oxidative stress and impaired antioxidant defense mechanisms may be the result of excess levels of glutamate to inducing excitotoxicity and neuronal cell death (Onley, 1969; Sattler & Tymianski, 2001).

[figure not shown]

Figure 2.2 Summary of evidence of antioxidant disturbances in OCD

Note. GSH-Px = glutathione peroxidase; MDA = malondialdehyde; SOD = superoxide dismutase; TBARS = thiobarbituric acid; TOA = total antioxidant status

^aKandemir, Abuhandan, Aksoy, Savik, & Kaya, 2013; ^bBehl, Swami, Sircar, Bhatia, & Banerjee, 2010; Ersan et al., 2006; Kuloglu et al., 2002; Ozdemir et al., 2009; Shohag et al., 2012; ^cChakraborty et al., 2009; ^dOzdemir et al., 2009; ^eErsan et al., 2006; Shohag et al., 2012. ^fAlici et al., 2016; ^g Shrivastava, Kar, Sharma, Mahdi, & Dalal, 2017 *Positively correlated with symptom severity **Trend only observed in Ersan et al., 2006 study, did not reach statistical significance.

2.2 Rationale

2.2.1 N-acetylcysteine (NAC)

N-acetylcysteine (NAC) is an acetylated form of the essential amino acid cysteine and has been used medicinally for over 50 years, initially in emergency departments for the treatment of paracetamol toxicity. NAC is considered a cysteine pro-drug which has been found to attenuate the synaptic release of glutamate in subcortical brain regions (via glutamate metabotropic autoreceptor 2/3 activation) and restore extracellular concentrations of glutamate in the nucleus accumbens (Baker et al., 2003; Madayag et al., 2007). The latter mechanism is postulated to be particularly beneficial for attenuation of compulsive behaviours, which both preclinical and clinical studies have highlighted NAC's ability to improve (Deepmala et al., 2015; Hurley et al., 2016; Kupchik et al., 2012; Madayag et al., 2007). Further, cysteine is the rate-limiting step for the potent endogenous antioxidant glutathione (GSH) and supplementation of NAC has been found to increase GSH in the bloodstream and brain (Lavoie et al., 2008, Dean, 2011; Das et al., 2013). Further, NACs modulation of glutamate and involvement in the production of GSH are believed to facilitate its neuroprotective effects and ability to enhance neurogenesis (Samuni, Goldstein, Dean, & Berk, 2013).

2.2.2 Pilot studies

Within the last 10 years, various case reports and clinical studies highlight promising, yet mixed effects of NAC for both pediatric and adult OCD (reviewed in Deepmala, 2015). However, many of these studies were underpowered (N = 40-50) and involved participants with varying severities and presentations of OCD, including treatment resistant populations.

To date, four RCTs investigating NAC for OCD in adult populations have been published. Two studies from Iran have revealed positive effects, the first highlighted a significant effect for NAC (2,400mg/day) over placebo from week-8, adjunctive to stable SSRIs or clomipramine, for improving symptoms in participants with OCD (N = 48, 75% women) (Afshar et al., 2012). Of note, the researchers classified these participants as treatment refractory, defined as failing to receive clinical benefits from two, 12-week courses of SSRIs or clomipramine. Another research group from Iran published additional positive effects in 2016, highlighting the ability of NAC augmentation (2,000mg/day) to potentiate the therapeutic effects of fluvoxamine (200mg) over

placebo + fluvoxamine over 10-weeks (Paydary et al., 2016). A third RCT was conducted in Brazil involving 40 adult patients who had failed to respond to at least one SSRI or clomipramine trial lasting for minimum 12 weeks (Costa et al., 2017). All participants experienced a reduction in their OCD symptoms (as per the Y-BOCS), however, NAC (3,000mg per day maximum dose from week-3 of the study) was not significant over placebo at the end of the 16-week intervention. In addition, our own pilot study (N = 44) published in 2015 revealed a non-significant effect for 3,000mg of NAC over placebo after 16-weeks (Sarris et al., 2015). A significant effect for improving compulsive symptoms was observed at week-12, however, this effect dissipated by week-16 end point. Our sample included participants with ranging severities and chronicity of OCD, and a post-moderator analysis revealed that NAC was more beneficial in less chronic presentations of OCD (<17 years duration), as well as those who were under the age of 34 (Sarris, Oliver, Camfield, & Dean, 2016). Further, previous clinical trials have revealed that NAC at doses beyond 3,000mg have elicited symptom improvement in attention-deficit hyperactivity disorder (ADHD), as well with lengthier administration of NAC (up to 6 months) in bipolar disorder (Berk et al., 2008; Berk et al., 2012; Garcia et al., 2013). Given these findings, and the many questions which remain regarding the benefits of NAC for differing symptom dimensions of OCD, treatment status, gender and required dose, a larger scale study to provide power to investigate these facets is warranted.

2.3 Potential Risks and Benefits

2.3.1 Potential Risks

The risks of participating include a breach of confidentially, side effects from taking the IP, discomfort when completing blood tests and/or the nature of the assessments involved in the study, including those conducted by the researcher as well as completed by the participants.

Participant's personal details will be collected during the baseline session of study (for contact purposes thereafter) and subsequent data will be de-identified. Although every effort will be made to maintain the anonymity of participants, a breach of confidentially is possible. See section 11.3 for further details regarding confidentially.

NAC may induce gastrointestinal side effects including mild abdominal pain or discomfort, heartburn, diarrhea, flatulence, nausea and cramps (Deepmala et al., 2015; Sarris et al., 2015).

Headaches, dizziness and skin rashes have also been reported in previous clinical studies (Ghanizadeh et al., 2017). However, specific to psychiatric research studies, only a small minority of participants have withdrawn due to side effects of NAC including a skin rash (n = 1), aggression (n = 1), severe heartburn (n = 1), neutropenia (with 6 grams of NAC, resolved when dose reduced to 2.4g; n = 1) and sensorineural deafness (n = 1) (Deepmala et al., 2015)

Participants may experience discomfort or bruising when having their blood taken during the study. The blood vessel may swell, or blood may clot in the blood vessel. Rarely, there could be a minor infection or bleeding.

Given that participants will be reviewing their mental, general and physical health in each of the study visits, some may find this psychologically distressing. To minimize these risks, all RAs involved in the assessment of participants will ensure that participants are adequately supported outside of the study, for example, advising them to maintain contact with their GP, psychiatrist and/or psychologist as required. In addition, participants who experience significant worsening in their mental health will be withdrawn from the study and referred for treatment. Further, during the informed consent discussion at baseline, the voluntary nature of the study and a participant's right to withdraw at any stage of the study will be highlighted.

2.3.2 Known Potential Benefits

Although the current available evidence of NAC in the treatment of OCD has revealed mixed results, several participants in previous clinical studies have experienced an improvement in their symptoms. Thus, in the current study, NAC (or placebo) may elicit a reduction in obsessive and compulsive behaviours for some individuals. Participants may also benefit from the knowledge that they are contributing to science and progressing the field of OCD research for other sufferers and their care givers. Participants will also be reimbursed for travel expenses totaling \$140-\$160 in the form of Coles/Myer gift cards (\$20 at each scheduled study visit, \$160 if all study visits are completed and if the baseline visits are completed on separate days). Upon completion of the 24-week study period, participants will have the option to receive three containers (120c in each container) of NAC free of charge.

3 OBJECTIVES

3.1 Study Objectives

This study seeks to elucidate the benefits of NAC augmentation (2-4 grams/day) compared to placebo in the treatment of OCD, in a 20-week, multicentre, randomised, double-blind, placebo controlled trial, with an additional 4-week, single blinded placebo run-out. The purpose of including a 4-week, placebo-run out is to asses any withdraw effects and/or sustained response of the NAC. It is hypothesised that NAC will be superior over placebo for improving OCD symptoms as measured by a reduction in Y-BOCS scores from baseline against each subsequent time point (W4, W8, W12, W16, W20 and W24). Additional benefits are anticipated for relieving anxiety as well as improving mood, functioning and overall quality of life. In addition, we will analyse the presence of single nucleotide polymorphisms (SNPs) related to glutamate and glutathione activity, which may serve as a predictor of treatment response to NAC in some individuals.

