3.2 Study Outcome Measures

3.2.1 Primary Outcome Measures

The primary outcome measure is the Yale Brown Obsessive-Compulsive Scale (Y-BOCS) which assesses the impact, frequency and severity of both obsessive and compulsive symptoms in OCD. The Y-BOCS will be administrated at each time point during the 24-week study (baseline 1 session, baseline 2 if more than 7 days post baseline 1, W4, W8, W12, W16, W20 and W24).

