8 STATISTICAL CONSIDERATIONS

8.1 Sample Size Considerations

A sample size of 200 participants (100 participants in each arm) are to be recruited and intention-to-treat principles will be applied to all data. A large sample of 200 participants is powered to detect a potential small to moderate effect size (f = 0.15) difference between NAC and placebo beyond treatment as usual, approximating a clinically significant 3 point reduction on the YBOCS (using all post-baseline data via intention-to-treat analysis). Based on an ANOVA model over seven time-points, a two tailed analysis with alpha=0.05, beta=0.80, and a critical F of 3.78; 200 participants (not including drop-outs) are required to detect a small to moderate effect size difference in Y-BOCS scale score between treatment and placebo.

The primary efficacy analysis will assess mean treatment group differences for the primary outcome measure (Y-BOCS) using a mixed-effects model, repeated measures approach (MMRM). Results from the analysis of dichotomous data (e.g. demographics data) will be presented as proportions with 95% confidence interval, and Fisher's Exact *p*-value where appropriate. Analysis of covariance (ANCOVA) will also be used to compare differences between treatment means in changes from baseline to week 20 last observation carried forward (LOCF) endpoint. The ANCOVA model will assess confounding covariates including intervention type (medication or psychological care), as well as age, gender, weight, physical activity levels, smoking and alcohol consumption.

Non-parametric statistics will be used when assumptions for parametric methods are violated. Effect sizes will be calculated using Cohen's d. All tests of treatment effects will be conducted using a two-tailed alpha level of 0.05 and 95% confidence intervals. Data will be analysed via SPSS 23.0.

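### The protocol fixes no single primary contrast or success rule for the Y-BOCS: six visits are named in the hypothesis and every treatment test is at 0.05

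*Protocol*

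**What the plan says.** - **Protocol 3.1 (Study Objectives)** hypothesises that NAC is superior to placebo, "measured by a reduction in Y-BOCS scores from baseline against each subsequent time point (W4, W8, W12, W16, W20 and W24"). The same section says that the four-week placebo run-out is there to look at withdrawal effects and sustained response.
- **Protocol 3.2.1 (Primary Outcome Measures)** names the scale and its schedule: "The Y-BOCS will be administrated at each time point during the 24-week study". It gives no primary visit.
- **Protocol 8.1 (Sample Size Considerations)** labels one analysis as primary: "The primary efficacy analysis will assess mean treatment group differences for the primary outcome measure (Y-BOCS) using a mixed-effects model, repeated measures approach (MMRM"). It does not say whether the test is an overall treatment effect, a treatment-by-visit interaction or a contrast at one visit.
- Section 8.1 adds an ANCOVA to "compare differences between treatment means in changes from baseline to week 20 last observation carried forward (LOCF) endpoint", without calling it secondary or a sensitivity analysis. It also states: "Non-parametric statistics will be used when assumptions for parametric methods are violated".
- On error control, section 8.1 has one sentence: "All tests of treatment effects will be conducted using a two-tailed alpha level of 0.05 and 95% confidence intervals". No hierarchy, adjustment or success rule appears.
- **Protocol 4.3.1 and 5.12** put all participants on placebo from week 20 to week 24.

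**The concern.** The protocol points three ways. Section 3.1 reads as six visit-wise claims, the sample-size paragraph as one between-group test over all time points, and the ANCOVA as week 20. If these disagree in the data, nothing in the document says which one decides the trial, so the choice could be made after the results are seen. At stake is the 5% error rate of the main conclusion of a Phase III trial.

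The primary contrast is not a detail that a protocol commonly leaves to the SAP. Including week 24 adds to the problem: by then neither arm has taken NAC for four weeks, so a difference there concerns persistence or withdrawal rather than on-treatment superiority.

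**Working it through.** **1. The plan's own figure.** Section 8.1 gives N = 200, seven time points, two-tailed alpha 0.05, power 0.80 (written as beta) and "powered to detect a potential small to moderate effect size (f = 0.15) difference between NAC and placebo". For one between-group F test over m visits with common correlation ρ:

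λ = f² × N × m / (1 + (m − 1)ρ), referred to F(1, N − 2).

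With m = 7 and ρ = 0.5 (ρ is not stated; assumed), λ = 0.0225 × 200 × 7 / (1 + 6 × 0.5) = 31.5 / 4 = 7.875. Power is 79.7% at N = 200, and 80% needs N = 202. The stated size is thus reproduced by **one** overall test. The stated critical F of 3.78 is not: F(1,198) is 3.89.

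**2. Error rate under each possible success rule.** Inputs: k = 6 visits (3.1), two-sided 0.05 each (8.1). The correlation between the visit test statistics is not in the protocol, so 0.5 to 0.8 is assumed and a wider range is shown.

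- *One pre-specified contrast, or one overall MMRM effect:* 5%.
- *All six visits required:* well below 5%, with no adjustment needed.
- *Any one visit suffices:* if independent, 1 − 0.95⁶ = 26.5%. For equally correlated normal statistics, simulated with |z| > 1.96:

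| Correlation | Six visits | Five on-treatment visits (W4–W20) |
|---|---|---|
| 0.5 | 20.8% | 18.2% |
| 0.6 | 18.7% | 16.6% |
| 0.7 | 16.4% | 14.8% |
| 0.8 | 14.0% | 12.7% |
| 0.95 | 8.9% | 8.5% |

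These rates are two-sided. For a false claim in favour of NAC at any of six visits, the rate is 10.4% at 0.5 and 7.0% at 0.8, against a nominal 2.5%.

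**3. What the further analyses add.** A patient-level null simulation used 100 per arm, an assumed 20% dropout and raw-score correlations of 0.5 to 0.9. It gave 18–24% for any of six visits, 19–26% with the LOCF ANCOVA as an extra route to success, and 20–27% with a rank test as well. The extra routes add about 1 to 3 percentage points, so the visits drive the figure.

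**4. Power of the two natural single contrasts at N = 200, f = 0.15 (d = 2f = 0.30).**

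- *Week 20 alone, unadjusted:* λ = 0.0225 × 200 = 4.5, power 56%.
- *Overall W4–W20 (m = 5, ρ = 0.5 assumed):* λ = 0.0225 × 200 × 5 / (1 + 4 × 0.5) = 22.5 / 3 = 7.5, power 78%. With ρ = 0.8, λ = 22.5 / 4.2 = 5.36, power 63%.

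A 3-point difference at d = 0.30 implies an SD of 3 / 0.30 = 10. An SD of 7, which the protocol does not give, would make d = 3 / 7 = 0.43 and week-20 power about 86%.

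**The case against.** The strongest reply is that section 8.1 already implies one test. It names a single primary analysis of group differences, and its sample size is reproduced by one between-group F test over all visits. On that reading the error rate is 5%. The word *each* in section 3.1 can also be read as requiring every visit, or as merely describing the repeated measurements that enter the model. Neither reading inflates anything.

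This stands as far as it goes. A reader might infer that a significant result at any visit, or by any method, supports the hypothesis, so that the false-positive rate simply is 14% to 21%. The protocol does not say that. The figure needs an any-visit rule and correlations that it does not state. What the reply does not do is close the gap: an overall effect is a plausible reading of section 8.1, but no sentence adopts it, and section 3.1 lists visits one by one, including one off treatment.

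Two further inferences are too strong.

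- The ANCOVA is not an equal rival to the MMRM, since only the MMRM is called primary. The ANCOVA is unranked. The non-parametric sentence is generic and not tied to the Y-BOCS, and its details may properly sit in an SAP.
- The pilot in section 2.2.2 might be taken as proof of the hazard: "A significant effect for improving compulsive symptoms was observed at week-12, however, this effect dissipated by week-16 end point". That result concerned compulsive symptoms, and the pilot was reported as non-significant at its end point. It shows that an effect at one visit can be transient, not that such an effect was presented as a positive trial.

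**Conclusion.** The concern holds in a conditional form. The protocol fixes neither a primary visit, nor an overall effect, nor a success rule, while naming six visits and testing all treatment effects at 0.05. If any one visit were taken as success, the two-sided false-positive rate would be about 14% to 21% for assumed correlations of 0.8 down to 0.5. It would be about 9% at 0.95, 26% under independence, and 13% to 18% for the five on-treatment visits with correlations of 0.8 to 0.5. If one overall MMRM effect is meant, it is 5%. The defect is that the document does not say which applies. Separately from any error rate, week 24 does not belong in the on-treatment superiority hypothesis.

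**What to change.** In sections 3.1, 3.2.1 and 8.1, name one MMRM contrast, tested at two-sided 0.05, as primary. Two choices fit the design:

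- **The NAC–placebo difference in Y-BOCS change at week 20**, the end of double-blind treatment and the visit the ANCOVA already uses.
- **The overall treatment effect across weeks 4 to 20**, the same kind of test as the sample-size model, though over five visits rather than seven time points.

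Declare the remaining visit estimates and the LOCF ANCOVA supportive, move week 24 to the run-out objective, and state the power for the chosen contrast with its assumed SD and between-visit correlation.

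The change is to wording only, but it exposes the power. For week 20, unadjusted power with 200 participants is 56% at the protocol's f = 0.15, before any gain from baseline adjustment. The 86% figure would need d = 0.43, which rests on an assumed SD of 7. The overall W4–W20 effect keeps about 78% at an assumed correlation of 0.5, falling to 63% at 0.8, but answers a question about average benefit over treatment rather than benefit at its end. All these figures assume 200 participants with complete data.
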